6.6.3 Safety data

With respect to safety evaluations, it is not planned to impute missing values. The only exceptions where imputation might be necessary for safety evaluation are AE dates and start and stop dates for concomitant medications. Missing or incomplete AE dates are imputed according to BI standards (see 001-MCG-156 RD-01 ($\frac{4}{2}$)).

Partial start and stop dates for concomitant medications and historical medication for UC will be imputed to enable subsequent calculation (but not for display) by the following "worst case" approach:

- If the day of the end date is missing, then the end date is set to last day of the month (or to the patient's trial completion date, if it is earlier than the last day of the month).
- If the day and month of the end date are missing then the end date is set to 31st of December of the year (or to the patient's trial completion date, if it is earlier than the 31st of December of the year).

- If the day of the start date is missing the start date is set to first day of the month (except for rescue medication, where the first dosing day will be used if first dosing happened in the same month).
- If the day and month of the start date are missing then the start date is set to 1st January of the year (except for rescue medication, where the first dosing day/month will be used if first dosing happened in the same year).
- All other cases need to be assessed by the trial team on an individual basis, using the above points as guidance.

If a concomitant medication or historical medication was ticked to be ongoing, it is expected that the end date is missing and will not be imputed for display purposes.

In principle safety data are displayed using the OR approach (meaning the presentation of data exactly as observed). However, for safety data that are displayed by time point (or visit) of measurement, the following approach will be used:

• Observed cases including rescue (OC-IR) approach will include all collected data (based on time windows as described in Section 6.7), with no imputation performed on the missing data and including all values measured after intake of a rescue medication.

6.6.4 PK data

Missing data and outliers of PK data are handled according to BI standards (see 001-MCS-36-472_RD-01) (5).

6.6.6 RNA sequencing data

The OC approach (cf. Section 6.6.2) will be used to present the RNA sequencing data.

6.6.7 Time since first diagnosis

For incomplete information on the date of first diagnosis, time since first diagnosis will be calculated as follows:

- If the year of first diagnosis is unknown, time since first diagnosis will be set to missing.
- If day and month of the first diagnosis are unknown, time since first diagnosis will be calculated as if diagnosed on the 30th June of that year.
- If only the day of the first diagnosis is unknown, time since first diagnosis will be calculated as if diagnosed on the 15th of that month.

6.7 BASELINE, TIME WINDOWS AND CALCULATED VISITS

Measurements reported with date and time and taken prior to start of administration of trial treatment will be considered pre-treatment values. Measurements reported with a date only (and no time) and taken on the day of first administration of trial treatment will also be considered pre-treatment values. These pre-treatment values will be assigned to visits according to the nominal visit number as recorded on the eCRF or as provided by the laboratory.

Baseline, unless otherwise specified, is defined as the last measurement collected prior to the start of administration of the trial treatment.

Measurements taken after start of administration of trial treatment will be considered ontreatment values or off-treatment values, based on the definition of the study analysis phases in Section 6.1, and will be assigned to visits for statistical analysis, if applicable, as defined below.

Analysis of AE data, concomitant medication or non-drug therapies, as well as use of rescue medication will not be based on visits. Frequency tables for these data will be using on-treatment data only. Therefore, no assignment to time windows will be necessary.

All other safety, efficacy and biomarker measurements will be assigned to visits based on extended time windows around the planned visit dates, defined relative to the day of first trial treatment (which is scheduled for Visit 2). These time windows are defined in Table 6.7: 1.

Visit	Planned			r	Time window (Days)		
number	Visit label	day	Window	Start	End	Start	End
/name			(per CTP)	(per CTP)	(per CTP)	(extended)	(extended)
V1a	Screening	-35 to -9	n/a				
V1b	Screening	-8 to -6	n/a				
V2	Baseline	Day 1	+/-0	1 ^A	1^{A}	≤1 ^A	1 ^A
V3	Week 1, Day	Day 4	+/-0	4	4	2^{A}	8
	4	•					
V4	Week 2	Day 15	+/- 1	14	16	9	21
V5	Week 4	Day 29	+/- 2	27	31	22	35
V6	Week 6	Day 43	+/- 2	41	45	36	49
V7	Week 8	Day 57	+/- 2	55	59	50	63
V8	Week 10	Day 71	+/- 2	69	73	64	77
EoT	Week 12	Day 85	-6 to [contact]
FU1	Week 18	Day 127	+/- 5	122	132	100	141
EoO ^B	Week 28	V7	+5			142	Day of last f
		+141days ^C					up value ^B

Table 6.7: 1Time windows for assignment of efficacy, safety lab, vital signs, biomarker,and RNA sequencing measurements to visits for statistical analysis

Proprietary confidential information © 2019 Boehringer Ingelheim International GmbH or one or more of its affiliated companies

Days are counted relative to the day of treatment, which is defined as Day 1. ^A Note that measurements made at Day 1 and assigned to the on-treatment period (because mistakenly made after start of infusion of trial treatment) via assessment on date and time (i.e. safety laboratory) will not be assigned to Visit 3. Such data will be listed only.

^B Note that measurements assigned to the Week 28/EoO visit may represent follow-up measurements (off-treatment period; cf. Table 6.1: 1). Both on-treatment and off-treatment data will be included for analysis of this visit.

Repeated and unscheduled efficacy, safety and biomarker measurements will be handled similarly to scheduled measurements and will also be assigned to a time window depending upon the date of measurement.

Only one observation per time window will be selected for statistical analysis at a particular visit – the value which is closest to the protocol planned visit day will be selected. If there are two observations which have the same difference in days to the planned day, but which are not measured on the same day, the later value will be selected. If there are two observations which are both closest to the planned day and were measured on the same day, the worst value will be selected.

Assignment of observations to visits based on time windows will be based on the nonimputed (observed) data after setting values after rescue medication intake to missing (if applicable, i.e. for the "OC" approach defined in Section 6.6.2). Visits which were not assigned a value based on time windows will not be imputed in this trial.

For derivation of the last value on treatment, minimum value on treatment, and maximum value on treatment, all on-treatment values (whether or not selected in any time window; see Table 6.1: 1 for definition of the on-treatment period) will be considered; these will be derived for analysis of laboratory and vital signs data. For identification of potentially clinically significant abnormal laboratory values, all values (whether or not selected in any time window) before the off-treatment period will be considered.

Tables and figures with results of the statistical analysis will only display visits at which the respective parameter was planned to be collected according to the CTP.

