Blood sampling for ADAs Stool sampling for faecal BMs	X ¹⁰	X X	X9			X9		X9		X		
Blood sampling for ADAs	X ¹⁰ X	l	X9			X9		X9		X		
Blood sampling for ADAs Stool sampling for faecal BMs Stool sampling for enteric pathogens		l	X9			X9		X9		X		

- 7. Only applicable for women of childbearing potential. A serum pregnancy test will be performed at screening. Urine pregnancy tests will be performed at all other visits indicated in the Flow Chart. In case of a positive urine pregnancy test, a serum pregnancy test will be done. Urine pregnancy testing should be done prior to administration of study drug in case there is dosing at study visits. Study drug should only be administered in case of a negative test result.
- 8. Includes clinical chemistry, haematology, coagulation and urinalysis assessments. Patient must be fasting for at least 8 hours prior to blood collection (except screening visit). If not fasted, mark on laboratory requisition.
- 9. At study visits with drug administration, blood samples must be obtained within approximately 2 hours prior to start of i.v. infusion.
- 10. Stool sampling will be done during screening period (Visit 1a or visit 1b, or at an unscheduled visit).
- 11. Diary will be used by the patient for the reporting of bowel movement frequency and rectal bleeding (blood in stool). The information will be used for the calculation of mayo score at the visits indicated in the Flow Chart. In addition, background UC medication will be recorded. Refer to Section 6.2.1 for more details.
- 12. Patients with early treatment discontinuation will complete EoT visit procedures and return for EoO visit 20 weeks (>5 half-lives of BI 655130) after the last dose of BI 655130.
- 13. Patients who complete regular treatment in study 1368-0004 will be offered to enter a long-term extension trial (1368-0017), which is currently in preparation. These patients can switch to trial 1368-0017 at EOT visit, and for these patients, their EoT visit will also be their EoO visit.
- 14. At Visit 2, a second sigmoidoscopy will be performed at 4 hours after start of the first study drug infusion to collect biopsy samples 4 hours post-dose. Also an additional blood sample for gene expression and methylation pattern analysis will be collected at 4 hours after start of infusion.

001-MCS-40-106-RD-03 (13.0) / Saved on: 05 Aug 2015

Trial Protocol

Page 8 of 82

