6.2.2 Treatment period(s)

The treatment period is from Visit 2 to End of Treatment (EoT) Visit.

Study related procedures will be performed as specified in the Flow Chart.

Pregnancy testing

Urine pregnancy testing for all women of child-bearing potential will be conducted on-site approximately every four weeks and must be negative to continue treatment. The pregnancy testing should be done **prior to** study drug administration. A positive urine test must be confirmed with a serum pregnancy test.

Blood sampling

Blood sampling (e.g., for safety lab, BMs) should be done **prior to** study drug administration and **prior to** sigmoidoscopy, if applicable. Patients should come in a fasted condition. If a patient comes in a non-fasted condition, where a fasting condition is required, the visit should be performed, the non-fasted condition documented on the laboratory requisition, and the patient reminded about the expected conditions.

At Visit 2, an additional blood sample for gene expression and methylation pattern will be collected at 4 hours after start of i.v. infusion.

Sigmoidoscopies

Sigmoidoscopies will be done after blood sampling and **prior to** study drug administration. During sigmoidoscopies, biopsies will be taken for endpoint evaluation at time points as indicated in the Flow Chart. Please refer to Section 5 of the ISF for further information on the collection and the processing of biopsies.

At Visit 2, an additional sigmoidoscopy will be done at 4 hours after start of i.v. infusion to collect additional biopsy samples.

PK and ADA sampling

At visits with study drug administration, blood sampling for PK assessments should be done within 2 hours **prior to** study drug administration.

Clinical monitoring after study drug administration:

The patient will be monitored for infusion reactions at the site for approximately 2 hours after end of infusion. At all visits with study drug administration, vital signs will be assessed predose, and at approximately 5 and 120 minutes after end of infusion. Unscheduled visits

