7.3.1 Primary endpoint analyses

For all genes, which are not excluded in the pre-processing step the Wald test (included as the default test for significance testing in the DESeq2 package) is conducted to identify whether this gene is deregulated or not for a certain time point.

Only one baseline value is included in the model, namely the last value before first drug administration, but all post-treatment values. The generalized linear model includes time as additional covariable (and also subject as covariable). So every time point is an additional design matrix element x_{jr} and the model fit leads (for every gene i) to β_{ir} estimates for each time point. To test changes from baseline the contrasts of these β coefficients (or more precisely the difference between post-treatment estimate and baseline) are divided by their estimated standard error, resulting in a z-statistic, which is compared to a standard normal distribution. Hereby the default option *lfcThreshold* = 0 is utilized, meaning a null hypothesis of no difference.

The Wald test results in a P-value and an FDR adjusted P-value for each gene and each posttreatment time point. A gene has a small P-value at a certain time point if there is a significant difference to the pre-treatment estimate, meaning an adjusted mean value clearly lower or higher compared to baseline. The calculation of the FDR adjusted P-value is (by default in the DESeq2 package) based on the Benjamini and Hochberg (P05-11198) approach (*pAdjustMethod* = "*BH*") combined with independent filtering (*independentFiltering* = *TRUE*). The independent filtering is based on the mean of normalized counts as a filtering statistic (R17-0127). A threshold on the filter statistic is found which optimizes the number of FDR adjusted P-values lower than a significance level of *alpha*=0.1 (default setting). In doing so, genes with very low counts at all time points are excluded and no FDR adjusted P-value is reported for these genes.

Beside the FDR adjusted P-value the Wald test calculates for every gene and every time point the difference in fold change compared to the baseline estimate. To get a conservative and stringent approach for the identification of deregulated genes both of these measurements, the FDR adjusted P-value based on the Wald test and the-fold change, are used to identify deregulated genes.

Definition of deregulated genes

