7.3 TREATMENT COMPLIANCE

Treatment compliance will be summarised overall via total volume infused (as a % of planned) for the FAS using descriptive statistics (N, mean, SD, minimum, median, maximum). For the patients who discontinued the study treatment prematurely only the visits on or before premature discontinuation will be used for the calculation of overall compliance.

The by visit compliance will be listed only.

The number and percentage of patients with the following overall compliance categories will be presented:

• "< 80% of planned",

- "80 to 120% of planned" and
- "> 120% of planned".

7.4 **PRIMARY ENDPOINTS**

The pre-processing of the raw read count values will be conducted as described in Section 7.3 of the CTP. The primary endpoint will be evaluated for the CAS. The analysis will be performed as defined in Section 7.3.1 of the CTP. The FDR adjusted P-value based on the Wald test and the log2 fold change, are used to identify deregulated genes.

Definition of deregulated genes

A gene is defined as deregulated at time point i if the FDR adjusted P-value of the Wald test is below 0.01 and if |fold change (time point i vs. baseline)| \geq 1.3.

The total number of deregulated genes per (post-baseline) time point (V2, V3, V4, V7 and EoT) will be reported.

The following sensitivity analyses may be conducted:

- The number of deregulated genes will be evaluated for the FAS in case this analysis set differs (with regard to RNA analyses) from the CAS
- In case the number of identified deregulated genes is very large (> 5000 deregulated genes at all time points) a smaller threshold for the FDR adjusted P-value will be considered
- In case the number of identified deregulated genes is empty (or includes less than 50 genes at all time points) the 50 genes with the smallest FDR adjusted P-values will be listed per (post-baseline) time point

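### Do the SAP 6.7 visit windows lose or misplace the planned 4-hour Visit 2 biopsy, one of the five primary-endpoint time points?

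*SAP*

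**What the plan says.** The protocol schedules the extra biopsy in note 14 of the flow chart: "At Visit 2, a second sigmoidoscopy will be performed at 4 hours after start of the first study drug infusion to collect biopsy samples". Protocol 6.2.2 repeats it. The other Visit 2 sigmoidoscopy is done before dosing.

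For the primary analysis, protocol 7.3.1 states: "Only one baseline value is included in the model, namely the last value before first drug administration, but all post-treatment values". SAP 7.4 says the analysis follows that section and lists the time points: "The total number of deregulated genes per (post-baseline) time point (V2, V3, V4, V7 and EoT) will be reported".

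Visit assignment is in SAP 6.7. It states that "All other safety, efficacy and biomarker measurements will be assigned to visits based on extended time windows around the planned visit dates", and the title of Table 6.7:1 includes "RNA sequencing measurements to visits for statistical analysis". SAP 6.6.6 leads to the same place: "The OC approach (cf. Section 6.6.2) will be used to present the RNA sequencing data", and the OC approach in SAP 6.6.2 relies on the windows of 6.7.

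In Table 6.7:1 the V2 row is labelled Baseline and its extended window ends on Day 1. The V3 window opens on Day 2. Within a window, "Only one observation per time window will be selected for statistical analysis at a particular visit". If two values are equally close to the planned day and fall on the same day, the worst is kept. Footnote A says that certain Day 1 values taken after the start of infusion are only listed. A Day 1 value with a date but no time counts as pre-treatment.

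**The concern.** SAP 6.7 treats V2 as baseline, while SAP 7.4 treats V2 as post-baseline. RNA sequencing is explicitly subject to the windows, and neither section states an exception for the 4-hour sample.

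A programmer working from the table alone could go wrong in three ways:

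- let the two Day 1 biopsies compete for one slot, with a worst-value tie rule that has no meaning for read counts;
- apply footnote A and only list the 4-hour sample;
- if no clock time were stored, class the 4-hour sample as pre-treatment and perhaps use it as baseline.

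At stake would be the earliest post-dose time point of the primary endpoint, in a trial whose primary objective is mechanism of action. That time point costs each patient an additional endoscopy.

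**Working it through.** **Inputs**

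- Planned patients: 10 (protocol 3.1).
- Biopsy occasions per patient (flow chart and note 14): V1b, V2 pre-dose, V2 at 4 hours, V3 (Day 4), V4 (Day 15), V7 (Day 57), EoT (Day 85).
- Extended windows (Table 6.7:1): V2 up to Day 1, V3 Days 2–8, V4 Days 9–21, V7 Days 50–63. The EoT bounds are not legible in the public text. Days 78–99 are assumed, because V8 ends on Day 77 and FU1 starts on Day 100.

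**The plan's own figure**

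SAP 7.4 names V2, V3, V4, V7 and EoT, which is 5 post-baseline time points. The protocol's post-dose biopsies are V2 at 4 hours, V3, V4, V7 and EoT, also 5. The lists match one to one only if V2 in SAP 7.4 is the 4-hour sample. With complete sampling, 5 × 10 = 50 post-baseline biopsies.

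**Placement by study day alone**

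| Biopsy | Day | Window reached |
|---|---|---|
| V1b | −8 to −6 | V2 |
| V2 pre-dose | 1 | V2 |
| V2 at 4 hours | 1 | V2 |
| V3 | 4 | V3 |
| V4 | 15 | V4 |
| V7 | 57 | V7 |
| EoT | 85 | EoT |

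On this placement only 4 post-dose biopsies have a row of their own, so 4 × 10 = 40, and 50 − 40 = 10 are unplaced. The same placement also puts the V1b biopsy in the V2 slot, because that window has no lower limit. That cannot be intended: protocol 7.3 compares the two pre-treatment biopsies to remove genes with high pre-treatment variability. Day-only placement therefore misreads the table, for a reason that has nothing to do with the 4-hour sample.

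**Placement in the order SAP 6.7 gives**

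1. Values timed before the start of treatment are pre-treatment and go to visits by nominal visit number. V1b stays V1b, and the pre-dose V2 sample stays V2.
2. Baseline is the last measurement before the start of administration, which is the pre-dose V2 sample. It is fixed here, before any window is used.
3. Values after the start of administration are on-treatment (Table 6.1:1 starts that period at the date and time of the first infusion). The 4-hour sample belongs here.
4. V3, V4, V7 and EoT samples go to their own windows. The 4-hour sample is the only on-treatment Day 1 biopsy, so there is no tie to break. SAP 7.4 reports it as V2.
5. Protocol 7.3.1 fits the one baseline with all post-treatment values.

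Result: 10 baseline samples and 50 of 50 post-baseline samples analysed.

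**The rules that might remove the 4-hour sample**

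- *Footnote A* concerns Day 1 values taken after infusion start by mistake, and identifies these as safety laboratory. A biopsy scheduled at 4 hours is neither. The end of SAP 6.7 also keeps visits at which a parameter was planned under the protocol, and this one was.
- *The date-only rule* needs a missing clock time. The sample is defined by time from the start of infusion, and nothing in the documents says that biopsy times go unrecorded.
- *The worst-value rule* does not operate, because the two Day 1 biopsies are already separated in steps 1 to 3.

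**The case for a change.** The strongest case for a change is that SAP 6.7 sends on-treatment values to the rows of Table 6.7:1, and no row is marked as post-dose on Day 1. Even if footnote A is set aside, the reader has to take the label from SAP 7.4 and not from the table. The revised SAP (06-DEC-19) is later than protocol version 4.0 (03 Apr 2019), which contains the 4-hour biopsy, so the table could have been brought into line. The correction would cost a few lines and would concern the primary endpoint.

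Part of this stands: the table does not name the 4-hour sample, and its only Day 1 label is Baseline. But the SAP does provide for the sample, in the section that governs the primary analysis. SAP 7.4 names V2 as post-baseline and points to protocol 7.3.1, which leaves no choice about which sample is baseline. SAP 6.7 defines baseline in the same way. A specific instruction for the primary endpoint takes precedence over a general visit-window table. SAP 6.1 also refers technical implementation to an ADS Plan that is not public, so it cannot be said that no assignment rule exists.

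**Conclusion.** The concern does not hold as a reason to change the plan. Table 6.7:1 is terse, but SAP 7.4, protocol 7.3.1 and the baseline definition in SAP 6.7 together give one workable handling: the pre-dose sample is baseline and the 4-hour sample is the post-baseline V2 result. All 5 time points and, with 10 patients and complete sampling, 50 of 50 post-baseline biopsies are analysed. The shortfall of 10 arises only if the order of steps in SAP 6.7 is skipped or a rule is stretched beyond its wording.

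Adding a row would write down what analysts would do anyway. No effect on the number of deregulated genes is shown, and the trial is exploratory with no confirmatory test (protocol 7.2). Labelling V2 in SAP 7.4 as the 4-hour sample would be clearer, but this is a matter of wording.

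The conclusion rests on one assumption about data capture: that the two Visit 2 samples carry a clock time or a nominal label that distinguishes them. The assumed EoT bounds do not affect the Day 1 question.

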5.3.2 Vital Signs

Vital signs will be assessed at all study visits. Vital signs assessment will include temperature, pulse rate, systolic/diastolic blood pressure and respiratory rate. Respiratory rate, pulse rate and blood pressure will be measured after the patient has been sitting comfortably for at least five minutes. All recordings should be made using the same type of blood pressure recording instrument on the same arm if possible.

At visits with study drug administration (Visits 2, 5 and 7) vital signs will be assessed predose, and additional evaluations will be taken at approximately 5 and 120 minutes after end of study drug administration.

The investigator should evaluate the clinical significance of the results. Clinically abnormal findings will be reported as baseline conditions or AEs.

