6.2 DETAILS OF TRIAL PROCEDURES AT SELECTED VISITS

Study procedures to be performed at each visit are listed in the Flow Chart and the respective protocol sections. Refer to Section 5 and Section 10 (Appendix) for explanations of procedures. Additional details on procedures at selected visits are provided below.

Measurement of vital signs should precede blood sampling and be assessed pre-dose at all dosing visits.

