7.8.3 Vital signs

The analyses of vital signs (blood pressure, pulse rate), body temperature, and body weight will be descriptive in nature.

Descriptive statistics of vital signs over time and for the difference from baseline (see Section 6.7) will be provided by treatment using on-treatment data only, including summaries of and will include the last value during on-treatment period, the minimum value during on-treatment period, and the maximum value during on-treatment period.

Clinically relevant findings in vital signs data will be reported as baseline conditions (at screening) or as AEs (during the trial) if judged clinically relevant by the investigator, and will be analysed as such.

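### SAP 6.7's same-day worst-value rule, applied as written, compares the worst of three vital-sign readings at V5 and V7 with a single pre-dose baseline, and no planned summary shows change around an infusion

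*SAP*

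**What the plan says.** **Readings.** At visits with drug administration (V2, V5, V7), Protocol 6.2 requires vital signs to "be assessed pre-dose at all dosing visits". Protocol 5.3.2 then says that "additional evaluations will be taken at approximately 5 and 120 minutes after end of study drug administration". That makes three planned readings on one day. Vital signs are also taken at every other visit, with one scheduled reading each.

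**Visit assignment.** The caption of SAP Table 6.7: 1 covers "assignment of efficacy, safety lab, vital signs, biomarker" and RNA sequencing data. SAP 6.6.3 applies these windows "for safety data that are displayed by time point (or visit) of measurement".

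**Selection.** SAP 6.7 states: "Only one observation per time window will be selected for statistical analysis at a particular visit". The value nearest the planned day is kept. When two observations are "both closest to the planned day and were measured on the same day, the worst value will be selected".

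**Baseline.** It "is defined as the last measurement collected prior to the start of administration of the trial treatment".

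**Display.** SAP 7.8.3 plans "Descriptive statistics of vital signs over time and for the difference from baseline", plus the last, minimum and maximum on-treatment values. It makes no exception to the selection rule and does not separate pre-dose, 5-minute and 120-minute readings.

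**The concern.** A worst-value rule is a reasonable tie-breaker for an accidental duplicate. Here it meets three readings planned for different purposes: one describes the patient before dosing, and two look for an effect of the infusion. Collapsing them to the worst has two consequences.

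- The by-visit change from baseline compares a selected extreme with an unselected single value, and does so only at V5 and V7. Those are the post-baseline visits where a reader would look for a drug effect.
- The planned summaries lose the timing relative to the infusion. The protocol names infusion reactions as an adverse event of special interest and relies on monitoring after each infusion, so this timing matters even in a descriptive trial of 10 patients.

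*Worst* is also undefined for blood pressure, pulse and temperature, where high and low values can both be unfavourable. The sign of any artefact therefore depends on an unstated programming choice.

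**Working it through.** The documents give no figure on this point, so there is none to reproduce.

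**Step 1: does the tie rule apply?** Distance to the planned day is counted in days. Three readings on one date are equally far from it, so they always tie. V5 (extended window Days 22 to 35) and V7 (Days 50 to 63) each hold three such readings. The rule speaks of two observations; three is its natural extension.

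**Step 2: what is baseline?** The last value before the first infusion, a single reading. This assumes that vital signs carry a clock time or time-point label. Under SAP 6.7, Day 1 measurements with a date only count as pre-treatment.

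**Step 3: where do the Day 1 post-infusion readings go?** The V2 window closes on Day 1 as baseline and the V3 window opens on Day 2. The planned 5- and 120-minute readings at V2 therefore have no by-visit slot.

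**Step 4: size of the selection effect.** Inputs:
- k = 3 readings (Protocol 5.3.2).
- s = within-visit SD of one reading. This is an assumption, not in the documents; 5 to 8 mmHg is used for systolic pressure.
- Independent errors, no true change, and *worst* meaning the highest value for every patient.

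For three independent normal readings:

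E[max of 3] − E[single] = 3 / (2√π) × s = 0.846 × s

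| s (mmHg) | Expected shift |
|---|---|
| 5 | 0.846 × 5 = 4.2 |
| 8 | 0.846 × 8 = 6.8 |

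If *worst* means lowest, the same figures apply with a minus sign. A simulation with 400,000 draws agrees: +5.07 (highest) and −5.09 (lowest) at s = 6, against 5.08 from the formula. A pre-dose reading minus baseline averaged −0.01 in that run.

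**Step 5: correlated readings.** If s is the SD of a single reading and same-day readings share a common correlation r, the factor becomes 0.846 × √(1 − r). At r = 0.5 it is 0.846 × 0.707 = 0.598, giving 3.0 mmHg (s = 5) to 4.8 mmHg (s = 8).

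**Step 6: scale at n = 10.** In the simulation at s = 6, the SD of the change (worst of three minus baseline) was 7.48, so the SE is 7.48 / √10 = 2.37. The artefact of 5.1 is 5.1 / 2.37 ≈ 2.1 SE. This allows for no other visit-to-visit variation, which would enlarge the SE.

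**Step 7: what the by-visit mean shows under a true effect.** Simulation at s = 6, with a true shift at the 5-minute reading only:

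| True 5-minute shift | By-visit change, *worst* = highest | By-visit change, *worst* = lowest | 5-minute minus same-visit pre-dose |
|---|---|---|---|
| −10 | +3.5 | −10.9 | −10.0 |
| 0 | +5.1 | −5.1 | 0.0 |
| +5 | +7.4 | −3.9 | +5.0 |
| +10 | +10.9 | −3.5 | +10.0 |

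The within-visit difference recovers the true shift. The selected value does not, and a shift opposite to the chosen direction disappears from the by-visit mean.

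**Step 8: direction varying by patient.** If *worst* means furthest from a normal range, some patients contribute their highest reading and others their lowest. For patients centred in the range the mean shift is zero by symmetry, and mainly the spread of the change is inflated.

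**The case against.** The best defence is that the rule is only a tie-breaker for duplicates. It is worded for two observations, follows a paragraph on repeated and unscheduled measurements, and SAP 6.6.3 leaves room for displays by time point. The ADS Plan and sponsor standards, not available here, may specify the handling. This narrows the point without removing it. SAP 6.7 names vital signs, allows one value per window and states no exception for planned time points. If the rule does not reach three readings, V5 and V7 have no rule at all, and an edit is still needed.

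Three stronger readings are tempting and should not be adopted.

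- *Post-infusion effects cannot be seen.* The last, minimum and maximum on-treatment values use all on-treatment readings, selected or not. All individual values are listed, and clinically relevant findings become adverse events. With 10 patients, each infusion can be read in the listings. What is missing is a summary around the infusion; the extremes pool a period running to 140 days after the last dose.
- *Day 1 post-infusion readings are relegated to listings by footnote A of Table 6.7: 1.* That footnote is worded for measurements taken after the start of infusion by mistake and refers to safety laboratory data. The planned vital signs are neither, and they still count towards the on-treatment extremes. They simply have no by-visit slot.
- *A mean shift is certain.* It needs one fixed direction of *worst*, which the SAP does not give.

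It also stands that vital signs are neither a primary nor a secondary endpoint, and that nothing is tested on them.

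**Conclusion.** The point holds in this limited form: wrong as written. The stated selection rule, followed literally, makes the V5 and V7 vital signs non-comparable with baseline and with the other visits. With one fixed direction the by-visit mean is displaced by up to about 0.85 within-visit SD, or 4.2 to 6.8 mmHg for an assumed SD of 5 to 8 mmHg. With a direction that varies by patient, the effect is mainly extra spread. The size rests on an assumed SD, on independent same-day readings (correlation reduces it), on extending a two-observation rule to three, and on vital signs being recorded with a time or time-point label.

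The consequence is a misleading descriptive safety table and the absence of any summary of change around an infusion. It is not a loss of the underlying safety data, and it does not touch the primary or secondary endpoints.

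**What to change.** In SAP 6.7 and 7.8.3:

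1. Use the pre-dose reading as the vital-sign visit value at V5 and V7, and as baseline at V2.
2. Summarise the 5- and 120-minute readings at V2, V5 and V7 as separate planned time points, each as change from the same-visit pre-dose value. This also gives the Day 1 post-infusion readings a place.
3. Limit the worst-value rule to unplanned repeats, and state the direction of *worst* for each parameter.

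The cost is one SAP sentence and one extra descriptive table from data already scheduled for collection. No assessment or trial procedure changes.
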